## 8.6 ADVERSE EVENTS AND SERIOUS ADVERSE EVENTS

### 8.6.1 DEFINITION OF ADVERSE EVENTS (AE)

Adverse event means any untoward medical occurrence associated with the use of an intervention in humans, whether or not considered intervention-related (21 CFR 312.32 (a)).

---

## 8.6.2 DEFINITION OF SERIOUS ADVERSE EVENTS (SAE)

An adverse event (AE) or suspected adverse reaction is considered "serious" if, in the view of either the investigator or sponsor, it results in any of the following outcomes: death, a life-threatening adverse event, inpatient hospitalization or prolongation of existing hospitalization, a persistent or significant incapacity or substantial disruption of the ability to conduct normal life functions, or a congenital anomaly/birth defect. Important medical events that may not result in death, be life-threatening, or require hospitalization may be considered serious when, based upon appropriate medical judgment, they may jeopardize the participant and may require medical or surgical intervention to prevent one of the outcomes listed in this definition.

---

## 8.6.3 CLASSIFICATION OF AN ADVERSE EVENT

---

### 8.6.3.1 SEVERITY OF EVENT

For adverse events (AEs) not included in the protocol defined grading system, the following guidelines will be used to describe severity.

- **Mild** – Events require minimal or no treatment and do not interfere with the participant's daily activities.
- **Moderate** – Events result in a low level of inconvenience or concern with the therapeutic measures. Moderate events may cause some interference with functioning.
- **Severe** – Events interrupt a participant's usual daily activity and may require systemic drug therapy or other treatment. Severe events are usually potentially life-threatening or incapacitating. Of note, the term "severe" does not necessarily equate to "serious".

---

### 8.6.3.2 RELATIONSHIP TO STUDY INTERVENTION

All adverse events (AEs) must have their relationship to study intervention assessed by the clinician who examines and evaluates the participant based on temporal relationship and his/her clinical judgment. The degree of certainty about causality will be graded using the categories below. In a clinical trial, the study product must always be suspect.

- **Related** – The AE is known to occur with the study intervention, there is a reasonable possibility that the study intervention caused the AE, or there is a temporal relationship between the study intervention and event. Reasonable possibility means that there is evidence to suggest a causal relationship between the study intervention and the AE.
- **Not Related** – There is not a reasonable possibility that the administration of the study intervention caused the event, there is no temporal relationship between the study intervention and event onset, or an alternate etiology has been established.

OR

- **Definitely Related** – There is clear evidence to suggest a causal relationship, and other possible contributing factors can be ruled out. The clinical event, including an abnormal laboratory test result, occurs in a plausible time relationship to study intervention administration and cannot be explained by concurrent disease or other drugs or chemicals. The response to withdrawal of the study intervention (dechallenge) should be

clinically plausible. The event must be pharmacologically or phenomenologically definitive, with use of a satisfactory rechallenge procedure if necessary.

- **Probably Related** – There is evidence to suggest a causal relationship, and the influence of other factors is unlikely. The clinical event, including an abnormal laboratory test result, occurs within a reasonable time after administration of the study intervention, is unlikely to be attributed to concurrent disease or other drugs or chemicals, and follows a clinically reasonable response on withdrawal (dechallenge). Rechallenge information is not required to fulfill this definition.
- **Potentially Related** – There is some evidence to suggest a causal relationship (e.g., the event occurred within a reasonable time after administration of the trial medication). However, other factors may have contributed to the event (e.g., the participant’s clinical condition, other concomitant events). Although an AE may rate only as “possibly related” soon after discovery, it can be flagged as requiring more information and later be upgraded to “probably related” or “definitely related”, as appropriate.
- **Unlikely to be related** – A clinical event, including an abnormal laboratory test result, whose temporal relationship to study intervention administration makes a causal relationship improbable (e.g., the event did not occur within a reasonable time after administration of the study intervention) and in which other drugs or chemicals or underlying disease provides plausible explanations (e.g., the participant’s clinical condition, other concomitant treatments).
- **Not Related** – The AE is completely independent of study intervention administration, and/or evidence exists that the event is definitely related to another etiology. There must be an alternative, definitive etiology documented by the clinician.

---

#### 8.6.3.3 EXPECTEDNESS

The principal investigator and independent safety monitor will be responsible for determining whether an adverse event (AE) is expected or unexpected. An AE will be considered unexpected if the nature, severity, or frequency of the event is not consistent with the risk information previously described for the study intervention or reported in the investigator brochure

---

#### 8.6.4 TIME PERIOD AND FREQUENCY FOR EVENT ASSESSMENT AND FOLLOW-UP

The occurrence of an adverse event (AE) or serious adverse event (SAE) may come to the attention of study personnel during study visits and interviews of a study participant presenting for medical care, or upon review by a study monitor.

All AEs including local and systemic reactions not meeting the criteria for SAEs will be captured on the appropriate case report form (CRF). Information to be collected includes event description, time of onset, clinician’s assessment of severity, relationship to study drug (assessed only by those with the training and authority to make a diagnosis), and time of resolution/stabilization of the event. All AEs occurring while on study must be documented appropriately regardless of relationship. All AEs will be followed to adequate resolution.

Any medical condition that is present at the time that the participant is screened will be considered as baseline and not reported as an AE. However, if the study participant’s condition deteriorates at any time during the study, it will be recorded as an AE.

Changes in the severity of an AE will be documented to allow an assessment of the duration of the event at each level of severity to be performed. AEs characterized as intermittent require documentation of onset and duration of each episode.

Research staff will record all reportable events with start dates occurring any time after informed consent is obtained until 28 days post randomization or hospital discharge, whichever comes sooner. At each study visit, the investigator will inquire about the occurrence of AE/SAEs since the last visit. Events will be followed until resolution or stabilization.

---

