## 3 OBJECTIVES AND ENDPOINTS

- **Primary Objective:** Determine the safety of administration of GSK2256294 in patients with aneurysmal SAH.

Frequencies of AEs and SAEs: We will compare AEs and SAEs between the drug and placebo groups. We will also compare daily safety labs (serum sodium, blood glucose, blood urea nitrogen (BUN), creatinine, hematocrit, peripheral white blood cell count) between the groups. Specific to this patient population, we will also specifically screen for disease related events including seizure, new onset cardiomyopathy, NSTEMI/STEMI, hyponatremia, hospital acquired infection, mechanical ventilation, and thromboembolic events. We will describe the severity of headache (on a daily scale of 0-10).

**Justification:** Prior phase 1 studies of GSK2256294 have been in healthy volunteers with limited physiologic monitoring. The most common adverse event was headache. We will assess safety in this critically ill patient population with special focus on common sequelae of subarachnoid hemorrhage.

- **Secondary Objective:** Determine the pharmacodynamic effects of administration of GSK2256294 in patients with aneurysmal SAH.

To evaluate the effect of enzymatic inhibition on circulating EETs levels, we will measure day 7 and day 10 serum EET/DHET ratios. EETs levels will be measured using liquid chromatography and mass spectroscopy.

To evaluate the possible effect of enzymatic inhibition on CSF EETs levels we will measure day 7 and day 10 CSF EET/DHET ratios, and compare the drug and placebo groups. We will also measure other lipid metabolic substrates of sEH at days 7 and day 10, specifically serum epoxyoctadecenoic acid (EPOME) and dihydroxyoctadec-12-enoic acid (DPOME), to assess sEH enzyme activity.

To evaluate more downstream effects on measures of endothelial injury and neuroinflammation, we will measure multiple biomarkers in the blood and CSF at day 7 and day 10 (Table 1). The biomarkers chosen are surrogate endpoints representing pathways of the inflammatory cascade associated with clinical endpoints in SAH.

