## TERTIARY ENDPOINT ASSESSMENTS

### **Discharge and Follow-up Assessments:**

At hospital discharge and 90-day follow-up, we will also measure objective clinical surrogate endpoints. The hospital discharge assessment will be abstracted from the patient medical record and obtained from patient interview. The 90-day follow-up assessment will be obtained from phone interview with the patient or their surrogate. We will collect the following information:

- **At Hospital Discharge:**
  - **Hospital length of stay**, in days
  - **New stroke on imaging:** We will review the last head CT or other brain imaging to detect the presence of a new area of cerebral infarction. We will define a cerebral infarction identified on hospital discharge that was not present on imaging between 24–48 hours after aneurysm occlusion, and not attributable to other causes such as surgical clipping or endovascular treatment. Hypodensities resulting from extraventricular drains or residual intraparenchymal hematomas will not be considered new strokes.
  - **Discharge disposition:** We will record the disposition from the hospital in one of the following categories: home, home with services, rehab, LTAC, SNF, hospice, death
  - **Modified Rankin Scale:** We will determine and record the mRS score from where 0 – no symptoms, 1 – no significant disability, able to carry out all usual activities despite some symptoms, 2 – slight disability. Able to look after own affairs without assistance, but unable to carry out all previous activities, 3 – moderate disability, requires some help, but able to walk unassisted, 4 – moderately severe disability, unable to attend to own bodily needs without assistance, and unable to walk unassisted, 5 – severe disability, requires constant nursing care and attention, bedridden, incontinent, 6 – deceased.
- **At 90-day follow up**
  - **Modified Rankin Scale**
  - **Extended Glasgow Outcome Scale (GOSE):** At 90 day follow up, we will determine the GOSE based on a structured interview of 19 questions detailed in the variable list and assessment tools. We will record the GOSE on a scale of 1-8 where 1 – deceased, 2 – vegetative state, 3 – low severe disability, 4 – upper severe disability, 5 – low moderate disability, 6 –upper moderate disability, 7 – low good recovery, 8 – upper good recovery.

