#### 9.4.3 ANALYSIS OF THE PRIMARY ENDPOINT

Safety will be assessed by clinical review of all relevant parameters including vital signs, laboratory values, adverse events, serious adverse events, disease related events, and mortality. Unless specified otherwise, the safety analyses will be conducted for the safety population.

Summary tables and listings will be provided for all reported adverse events, defined as adverse events that start on or after the first administration of study drug. The reported adverse event term will be assigned a standardized preferred term.

Adverse events will be summarized based on the number and percentage of patients experiencing the event. In the event a patient experiences repeat episodes of the same adverse event, then the event with the highest severity grade and strongest causal relationship to study treatment will be used for purposes of incidence tabulations. Tabular summaries will be provided for all adverse events, the relationship to study drug treatment the maximum severity grade, action taken, and whether the event qualified as SAE or not.

Daily safety laboratory test results will be summarized in a descriptive manner by calculating the mean, standard deviation, median, and range. Directional shifts (comparing baseline grade with worst post-baseline grade) will be analyzed using standard shift tables. The shift table will present directional shifts from baseline to above or below the laboratory standard normal range using the maximum increase and/or decrease observed throughout the course of treatment/observation.

Vital signs will be summarized in a descriptive manner by calculating the mean, standard deviation, median, and range in the same manner described for laboratory values.

All deaths will be reported in a patient listing, which will include the primary cause of death and the number of days between the date of the last dose of study drug and death.

---

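### Section 8.6.4 gives conflicting end points for recording AEs and SAEs and 9.4.3 names none; if the discharge cut-off is followed, non-fatal events after discharge are missed and observation time depends on length of stay

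*Combined protocol and SAP*

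**What the plan says.** Section 8.6.4 has one explicit stopping rule for event start dates: from informed consent "until 28 days post randomization or hospital discharge, whichever comes sooner". Three other sentences in the section do not stop there:

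- "All AEs occurring while on study must be documented appropriately regardless of relationship"
- a worsening of the participant's state is covered without limit: "condition deteriorates at any time during the study, it will be recorded as an AE"
- "At each study visit, the investigator will inquire about the occurrence of AE/SAEs since the last visit"

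The synopsis gives a participant duration of 90 days, and section 7.3 refers to the day-90 contact as a visit. The tertiary endpoint assessments describe it thus: "The 90-day follow-up assessment will be obtained from phone interview with the patient or their surrogate". The items listed for it there are the mRS and GOSE.

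On analysis, section 3 states: "We will compare AEs and SAEs between the drug and placebo groups". Section 9.4.3 gives the AE tables a starting point only, "defined as adverse events that start on or after the first administration of study drug", and a crude measure: "Adverse events will be summarized based on the number and percentage of patients experiencing the event". It adds listings, severity, relationship, action taken and seriousness, but no end date, common period or time at risk.

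**The concern.** Safety is the primary objective, and the planned measure is a percentage of patients with an event. Such a percentage means something only over a stated period. Under the cut-off sentence the period is each patient's own hospital stay, capped at day 28. Stay reflects clinical course and is itself a tertiary endpoint, so the sickest patients are watched longest. Staff could also stop at discharge, at day 28 or at day 90 and cite 8.6.4 for each choice.

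The stakes are non-fatal events that begin after discharge, possibly while drug is still in the body. Section 2.3.2 calls this the first study of the drug in critically ill patients, and section 2.3.1 says that the existing safety database is limited. The interpretability of the between-arm comparison is a lesser stake.

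**Working it through.** The plan states no event rate or expected length of stay, and section 9.2 gives no formula, so there is no plan figure to reproduce. The check has four steps.

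**1. The texts side by side.** For a patient discharged on day 14, the cut-off sentence ends recording on day 14. The sentences on events during the study run to day 90. The visit sentence also runs to day 90 if the visit named in 7.3 is a study visit in the sense of 8.6.4. Section 9.4.3 does not choose between them. Under the cut-off, this patient is observed 14/28 = half as long as one still in hospital on day 28.

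**2. Drug remaining.** Section 2.2 gives a half-life of 20-30 h. Taking five half-lives as the convention for clearance:

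- 5 × 20 h = 100 h = 4.2 days; 5 × 30 h = 150 h = 6.3 days after the last dose.
- With first-order elimination, the fraction left at 24 h is 0.5^(24/20) = 0.44 to 0.5^(24/30) = 0.57. At 48 h it is 0.19 to 0.33.

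Section 7.1 foresees early discharge. How many patients leave inside this interval cannot be derived, because no stay is given; the 10-14 days in section 2.1 is ICU monitoring, not time to discharge.

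**3. How much is unobserved under the cut-off.** Assumptions: gamma-distributed stays from randomization with mean 14, 18 or 21 days and SD 6, 8 or 10, the same in both arms, 15 per arm, no deaths. By simulation:

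- Discharge, not day 28, ends recording for 79-98% of patients.
- On average 26-59% of days 11-28 is observed.

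**4. Effect on the reported percentages.** Assume a constant hazard λ, equal in both arms, with 30% risk by day 28: λ = -ln(0.70)/28 = 0.0127 per day. Recorded risk by day t is 1 - exp(-λt).

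- Day 14: 16.3%. Day 21: 23.5%. If everyone in one arm were observed 14 days and everyone in the other 21, the percentages would differ by 7.1 points, or 2.5 against 3.5 patients of 15.
- Against 18 and 22 days the difference is 3.9 points.
- With stays drawn as in step 3, so that arms differ only by chance, the absolute shift in expected percentage averages about 1.5-2.5 points across the nine combinations of mean and SD, with a 95th percentile of about 4-6 points.
- For scale, the sampling standard error of a difference at 30% with 15 per arm is √(2 × 0.30 × 0.70/15) = 0.167, about 17 points.

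**The case against.** **Post-discharge inquiry may already be planned.** Section 7.3 calls the day-90 contact a visit and 8.6.4 asks about events at each visit. A reader might infer that the plan never looks for non-fatal events after discharge; the documents do not support that. The Schedule of Activities and the variable list, which could settle it, are not in the text available. The term for reportable events is also undefined, so the cut-off might have been meant for reporting only. This stands, and it makes the defect a conflict of wording with a conditional consequence. It does not remove the conflict, and the tables still lack an end.

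**The bias is small.** A reader might infer that the AE percentages are materially biased between arms. That needs stay or in-hospital death to differ by arm, and the documents give no evidence of such a difference. The chance shift in step 4 is far below sampling error, and 9.4.3 plans clinical review, not a test. Patient-days in days 11-28 do differ 1.5-fold or more in 32-40% of simulated trials at a mean stay of 14 days, but those stays send 27-42% of patients home before day 10, which sits badly with section 7.1. Limiting the same draws to stays of at least 10 days gives about 12-15%. This objection stands.

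**Not everything stops at discharge.** Deaths are sought afterwards (5.4, 7.3), and 8.6.6 puts no discharge limit on unexpected SAEs that become known. Daily assessments belong to days 1-10 (8.4.1) and are cut short only if the patient leaves, dies or stops drug earlier. This stands and narrows the point to non-fatal AEs and SAEs, mainly after day 10.

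**Rates per in-hospital day do not cure the dependence.** Suppose hazards are equal in both arms, half the patients are severe with three times the hazard and stay to day 28, and drug shortens only the milder patients' stay, from 18 to 13 days. Counting days beyond day 10, the rate in units of the milder hazard is (8 + 3 × 18)/(8 + 18) = 2.38 on placebo and (3 + 3 × 18)/(3 + 18) = 2.71 on drug, about 14% higher with no drug effect on events. This also stands, so such rates need a caution beside them.

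**Conclusion.** The point holds as a contradiction within 8.6.4 together with a missing end point in 9.4.3. It should be corrected, since safety is the primary objective and the repair is cheap. The unequal, stay-dependent observation follows only if the discharge cut-off is what staff apply. In that case the main cost is unrecorded non-fatal events after discharge, including some within the 4.2-6.3 days in which drug may still be present. A large distortion of the arm comparison is not shown. If events cluster in days 1-10, the percentages hardly move.

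The contradiction rests on the text alone. The sizes rest on assumed stays, an assumed 30% risk, a constant hazard and the five-half-life convention. Length of stay will be shown by arm (9.1, 9.4.4), so an imbalance would be visible, but that neither puts the percentages on a common period nor recovers missed events. Confidence is medium, because the Schedule of Activities could not be read.

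**What to change.** 1. **Section 8.6.4:** replace the conflicting sentences with one recording window, define which events it covers, and state that AE/SAE inquiry is part of the 90-day visit.

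2. **Section 8.6.4:** collect SAEs with onset up to day 28 for every participant, whether or not discharged, using the record network already searched for deaths (5.4) and the existing 90-day call. Report post-discharge SAEs separately from in-hospital events.

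3. **Section 9.4.3:** name the window and add wording such as: AEs, SAEs and disease-related events will be tabulated by arm for study days 1-10 and days 11-28, giving the number of patients and patient-days observed in each period beside the percentages; in-hospital rates for days 11-28 are conditional on remaining in hospital and are descriptive only. Days 1-10 are nearly common to all patients.

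**Cost.** Items 1 and 3 are wording; onset times and length of stay are already collected. Item 2 adds one record check and a few questions per participant. Its weakness is incomplete ascertainment: outside records will vary with where the patient goes, the call comes 90 - 28 = 62 days after the window closes, and section 2.1 says that cognitive dysfunction and disability may affect more than half of survivors. Post-discharge SAEs will therefore be under-counted, which is why they should be shown apart.

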#### 8.6.5 ADVERSE EVENT REPORTING

Summaries of adverse events will be recorded for each study visit, and reported to the independent safety monitor, the institutional review board, and the study sponsor annually, in accordance with regulatory requirements. Expected disease-related events common in the study population which will not be reported per the standard process for reporting include: seizure, need for intervention to manage DCI, new onset cardiomyopathy, hypotension, hypertension, NSTEMI/STEMI, hyponatremia, hospital acquired infection, respiratory failure requiring mechanical ventilation, therapeutic antimicrobial use and indication, thromboembolic events, and disease related death.

---

#### 8.6.6 SERIOUS ADVERSE EVENT REPORTING

The investigators will report within 72 hours of knowledge to the independent safety monitor, any unexpected serious adverse event, whether or not considered study intervention related, including those listed in the protocol or investigator brochure and must include an assessment of whether there is a reasonable possibility that the study intervention caused the event. Study endpoints that are serious adverse events (e.g., all-cause mortality) must be reported in accordance with the protocol unless there is evidence suggesting a causal relationship between the study intervention and the event (e.g., death from anaphylaxis). In that case, the investigator must immediately report the event to the independent safety monitor and to the IRB

All serious adverse events (SAEs) will be followed until satisfactory resolution or until the site investigator deems the event to be chronic or the participant is stable.

The investigators will be responsible for notifying the Food and Drug Administration (FDA) and GlaxoSmithKline of any unexpected fatal or life-threatening suspected adverse reaction as soon as possible, but in no case later than 7 calendar days after the sponsor's initial receipt of the information.

---

